5.4 Other Endpoints

CCI

CCI

- Number and percent of subjects permanently discontinued from the study due to hyperglycemia;

CCI

5.5 Safety Endpoints

- Number and percent of subjects (including number of events) experiencing treatment-emergent AEs (TEAEs) and serious AEs (SAEs);
- Number and percent of subjects experiencing AEs of special interest (AESIs) as defined by protocol (GI events such as nausea, vomiting, and diarrhea; major CV events; hypoglycemia; injection site reactions; hypersensitivity reactions; and pancreatic events);
- Vital signs (blood pressure and pulse rate);
- Safety laboratory measures (chemistry, hematology, and urinalysis); and
- 12-lead electrocardiograms (ECG).

6 STATISTICAL METHODOLOGY

6.1 Sample Size Determination

Subjects will be randomized at an approximate ratio of 1.75:1 (OPK-88003:placebo). A sample size of 48 subjects in the active arm and 27 subjects in the placebo arm will provide at least 90% power to detect superior glycemetic control over placebo represented by -0.8% in HbA1c levels after 30 weeks of treatment. This assumes a common standard deviation (SD) of 1.0% and a two-sided alpha of 0.05. The assumptions are based on variability in previously obtained HbA1c results from the OPK-88003 phase 2 trial XNAA.

Approximately 110 subjects were enrolled in an effort to obtain 88 completed subjects (56 subjects completing in the active arm and 32 subjects completing in the placebo arm).

6.2 Baseline, Endpoint, and Other Statistical Considerations

The clinical statistical efficacy and safety analyses will be performed by Medpace.

First dose of study drug refers to the first dose of blinded study drug (Week 0 Day 1).

Baseline will be the measurement at Week 0 Day 1. If missing, the last valid measurement prior to the first administration of study drug will be used as baseline.

Any measurements/events that occur after the subject started rescue therapy will not be included in the efficacy analyses.

Unless specified otherwise, treatment groups will be OPK-88003 and placebo for summaries and analyses. Additional explorations may be done by OPK-88003 dose.

Descriptive statistics (n, mean, standard deviation, median, minimum, and maximum) will be used to summarize the continuous efficacy and safety data by treatment group. The count and frequency will be used to tabulate categorical measurements.

Data will be used as it is reported. LOCF may be used when specified. The value must be collected within the last dose date +10, inclusive, in order to be used as LOCF. Where specified, LOCF_H (for subjects that have discontinued early due to hyperglycemia) or LOCF_{All} (for all subjects) may be used.

No adjustments for multiplicity will be performed. All tests of treatment effects will be conducted at a two-sided alpha level of 0.05 and/or two-sided 95% confidence interval (CI), unless otherwise stated.

Analysis Visit Windows

For all efficacy and safety assessments, analysis visits will be assigned according to the actual study day, calculated as the assessment date – first dose date for assessments prior to the first dose date and assessment date – first dose date +1 for assessments on or after the first dose date. The analysis visit windows will be defined as the halfway point between the target visit days:

Analysis Visit	Target Visit Day	Analysis Visit Window (Days)
Visit 1 (Screening)	N/A	N/A
Baseline	1	≤ 1
Visit 3 (Week 1)	8	2 – 18
Visit 4 (Week 4)	29	19 – 43
Visit 5 (Week 8)	57	44 – 60

Analysis Visit	Target Visit Day	Analysis Visit Window (Days)
Visit 6 (Week 9)	64	61 – 67
Visit 7 (Week 10)	71	68 – 74
Visit 8 (Week 11)	78	75 – 81
Visit 9 (Week 12)	85	82 – 99
Visit 10 (Week 16)	113	100 – 134
Visit 11 (Week 22)	155	135 – 169
Visit 12 (Week 26)	183	170 – 197
Visit 13 (Week 30)	211	198 to \leq last dose date + 10
Visit 14 (Week 34/Follow-up)	239	N/A

If there is more than one assessment within a visit window, then the analysis visit will be assigned by the following priorities:

1. Use the visit with the matching visit label
2. Use the visit closest to the target visit day. In the case of ties, use the later assessment.

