#### **9.4.8 Visit 12 (Week 26±4 Days) Target Dose**

At this visit, the following study activities will be performed:

- Fasting weight
- Vital signs (prior to blood draw and study drug administration)
- Blood draw:
  - Fasting glucose
- CCI [REDACTED]
- AE assessment
- Subject diary review
- Concomitant medication review
- Distribute test strips as needed
- Drug accountability
- Study drug dispensed to subject
- Dose administration
- Lifestyle counseling
- CCI [REDACTED]  
[REDACTED]

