#### **9.4.9 Visit 13 (Week 30±4 Days) End of Treatment**

At this visit, the following study activities will be performed:

- Fasting weight, CCI [REDACTED]
- 12-lead ECG (triplicate)
- Vital signs (supine blood pressure and pulse rate will be assessed following 12-lead ECG and prior to any blood draws)
- Blood samples:
  - Fasting glucose
  - Serum chemistry
  - Serum calcitonin
  - Hematology
  - CCI [REDACTED]
  - HbA1c
  - CCI [REDACTED]
  - Immunogenicity
- CCI [REDACTED]
- Urinalysis
- AE assessment
- Subject diary review
- Concomitant medication review
- Distribute test strips as needed
- Drug accountability
- Lifestyle counseling
- CCI [REDACTED]  
[REDACTED]

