| Lifestyle counseling m  |           | X                |     | X    |            | X           |            |                         |      |      |      | X    |            | X     | X     | X     | X     |                  |    |     |
| Subject training n      |           | X                |     |      |            |             |            |                         |      |      |      |      |            |       |       |       |       |                  |    |     |
| SMBG o                  |           |                  | X   | X    |            | X           |            |                         | X    | X    | X    | X    |            | X     | X     | X     | X     |                  |    |     |
| Randomization                      |           | X                |     |      |            |             |            |                         |      |      |      |      |            |       |       |       |       |                  |    |     |
| At-visit dosing p       |           | X                | X   | X    |            | X           |            |                         | X    | X    | X    | X    |            | X     | X     | X     |       |                  |    |     |
| Dispense study drug to subject     |           |                  | X   | X    |            |             |            |                         |      |      |      | X    |            | X     | X     | X     |       |                  |    |     |
| Drug accountability                |           |                  |     | X    |            | X           |            |                         | X    | X    | X    | X    |            | X     | X     | X     | X     |                  | X  |     |
| CCI                                |           |                  |     |      |            |             |            |                         |      |      |      |      |            |       |       |       |       |                  |    |     |
| AE assessment                      |           | X                | X   | X    | X          | X           | X          | X                       | X    | X    | X    | X    | X          | X     | X     | X     | X     | X                | X  | X   |

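### SAP 6.2 ends the Week 30 window at last dose + 10 days, which misses the last permitted Visit 13 day on nominal dosing and up to 5 days if the final doses follow an early Visit 12

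*SAP*

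**What the plan says.** SAP 6.2 states that "analysis visits will be assigned according to the actual study day", and then that "The analysis visit windows will be defined as the halfway point between the target visit days". In the table that follows, the Week 30 row (Visit 13, target Day 211) opens on Day 198 but has no study-day upper limit. It ends at "last dose date +10" days, inclusive. The follow-up row (Visit 14) has no window. The same section limits carried-forward values: "The value must be collected within the last dose date +10, inclusive, in order to be used as LOCF". The preference for a matching visit label applies only in one situation: "If there is more than one assessment within a visit window".

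The protocol schedules the endpoint visit as "Visit 13 (Week 30±4 Days) End of Treatment" and the last dosing visit as "Visit 12 (Week 26±4 Days) Target Dose". In Appendix 1 the row "At-visit dosing" runs from Visit 2 to Visit 12 and is empty at Visit 13; section 9.4.9 lists no dose either. Protocol 6.5 gives weekly dosing for 4 + 4 + 22 weeks. HbA1c is drawn at Weeks 22 and 30 but not at Week 26 (Appendix 1; SAP 5.3). SAP 5.1 leaves a missing Week 30 value unimputed unless the subject discontinued early because of hyperglycemia.

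**The concern.** One document sets the primary-endpoint visit by study day, and the other closes its analysis window by days since the last dose. Because no dose is given at Visit 13, the two limits can separate. A subject can then be fully dosed, attend inside the protocol window and have an HbA1c result, yet that result falls after the analysis window has closed.

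The value is then lost to the Week 30 MMRM contrast (SAP 6.9.1) and to the Week 30 HbA1c responder comparison (SAP 6.9.2.1). In the supportive LOCF ANCOVA it would usually be replaced by the Week 22 value, whose target day is 211 − 155 = 56 days earlier. The same table row also governs Week 30 FPG and body weight. SAP 8.2 already reports more early discontinuation than expected, so there is little reason to give up endpoint values that were collected on schedule.

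**Working it through.** **Inputs.** Target days and windows: SAP 6.2. Visit 12 on Day 183 ± 4 (Days 179 to 187) and Visit 13 on Day 211 ± 4 (Days 207 to 215): Protocol Appendix 1. Thirty weekly doses starting on Day 1: Protocol 6.5.

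**Step 1: reproduce the SAP's window rule.** The midpoints of adjacent target days, rounded down, are 18, 43, 60, 67, 74, 81, 99, 134, 169 and 197. These match all ten upper limits from Visit 3 to Visit 12. For Visit 13 the rule would give (211 + 239)/2 = Day 225. The table uses last dose + 10 there instead, and the readable text gives no reason.

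**Step 2: nominal calendar, no dose missed.** Dose 30 falls on Day 1 + 29 × 7 = 204. The window closes on 204 + 10 = Day 214. Of the nine permitted days, only Day 215 is outside. Target Day 211 has 3 days to spare.

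**Step 3: final doses linked to Visit 12, no dose missed.** The Visit 12 dose is followed by three weekly home doses, so the last dose is Visit 12 + 21 and the window closes on Visit 12 + 31.

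| Visit 12 day | Last dose | Window closes | Permitted Visit 13 days lost |
|---|---|---|---|
| 179 | 200 | 210 | 5 (211–215) |
| 180 | 201 | 211 | 4 (212–215) |
| 181 | 202 | 212 | 3 (213–215) |
| 182 | 203 | 213 | 2 (214–215) |
| 183 | 204 | 214 | 1 (215) |
| 184–187 | 205–208 | 215–218 | 0 |

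In total, 5 + 4 + 3 + 2 + 1 = 15 of 9 × 9 = 81 day combinations are lost.

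**Step 4: are the extreme rows reachable?** On the nominal calendar the Week 25 dose is on Day 1 + 25 × 7 = 176. A Visit 12 dose on Day 179 comes 3 days later, and on Day 180 it comes 4 days later. Protocol 6.7 bars a dose within four days of the previous one. That rules out Day 179, and Day 180 too if the fourth day counts, unless earlier doses had also moved forward. These two rows supply 5 + 4 = 9 of the 15 combinations and the only case in which Day 211 itself is lost.

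**Step 5: is the value recovered elsewhere?** The label rule chooses among assessments already inside one window, so it cannot bring in one that lies outside. LOCF has the same +10 limit. Visit 14 has no window. SAP 5.1 imputes only for discontinuation due to hyperglycemia.

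**Step 6: what limit would cover Day 215?** Nominal calendar: 215 − 204 = 11 days. Visit-linked, earliest Visit 12: 215 − 200 = 15 days. Limits of +10, +11, +12, +13, +14 and +15 lose 15, 10, 6, 3, 1 and 0 of the 81 visit-linked combinations.

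**The case against.** The strongest reply is that the +10 limit is a deliberate on-treatment rule. SAP 6.2 applies the same limit to LOCF and also drops values after rescue therapy. A halfway bound at Day 225 could admit off-drug follow-up samples. Much of this stands: an on-treatment limit is a legitimate choice, and departing from the halfway rule has an evident use. It does not explain why the limit is shorter than the 11 days that the protocol's own schedule allows a fully dosed subject on the nominal calendar.

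Three stronger readings are tempting, and the documents do not support them.

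- **That the window is always too short.** It is not. On visit-linked dosing there is no shortfall from Visit 12 Day 184 onward, and on nominal dosing eight of nine permitted days are kept. The larger shortfalls need home doses re-anchored to an early Visit 12, whereas Protocol 6.7 advises the same day each week.
- **That 15 of 81 (18.5%) is a share of subjects, from which a power loss follows.** It counts day combinations. The documents give no distribution of visit days, and the combinations are not equally likely.
- **That losing values from subjects who skipped final doses is part of the error.** With only the last dose skipped on the nominal calendar, the window closes on 197 + 10 = Day 207, and a Day 211 sample is 14 days after the last dose. Excluding it is what an on-treatment limit is meant to do. Such a subject still counts as compliant, since up to four misses are allowed outside the rule on consecutive doses during escalation. That does not oblige the SAP to use the value.

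It is also true that the MMRM loses the Week 30 value and not the subject, and that LOCF for all subjects enters only supportive analyses.

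**Conclusion.** The conflict is real but small. With all 30 doses on the nominal calendar, the Week 30 window closes one day before the protocol's Visit 13 window. With final doses taken weekly from Visit 12, the shortfall is 0 to 5 days, and its upper end also requires earlier doses to have shifted. On the literal text, an affected HbA1c value belongs to no efficacy visit and nothing restores it.

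This rests on reading the window table as written, on no dose at Visit 13, and on the two dosing patterns shown. How many subjects are affected cannot be known from the documents. Neither bias nor loss of power is shown. The correction is worth making because it concerns observed values of the primary endpoint and is easy to make.

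**What to change.** Before unblinding, reconcile the Week 30 upper bound with the Visit 13 window:

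- Keep Visit 13-labelled assessments of subjects who completed dosing through Day 215. Alternatively, widen the on-treatment limit for Visit 13 to +11 days (nominal dosing) or up to +15 days (visit-linked dosing).
- Leave last dose + 10 in place for LOCF and for early-termination assessments, so that on-treatment early-termination values from Day 198 onward stay usable.
- Keep Visit 14 and other follow-up assessments out of Week 30.
- Report, by arm, how many observed Week 30 values the +10 limit removes, and repeat the primary analysis under that limit as a sensitivity analysis.
- State separately whether values from subjects who skipped final doses count. That is an estimand decision.

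The cost is one table cell and one or two sentences, with no new data. The downside is that a few values taken 11 to 15 days after the last dose are kept, which matters more for FPG than for HbA1c. A blanket widening would also admit some values after a skipped final dose: with the last dose on Day 197, a +15 limit closes on Day 212. The version tied to the Visit 13 label and completed dosing avoids this.

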6.3 Analysis Populations

6.3.1 ITT Population

The Intent-to-Treat (ITT) Population is defined as all randomized subjects.

6.3.2 mITT Population

The Modified Intent-to-Treat (mITT) Population is defined as all randomized subjects who received at least one dose of study drug and have baseline and at least one valid post-baseline measurement for the primary outcome. Statistical analyses (including the primary analysis) will be conducted on the mITT Population. In the event of allocation errors, subjects will be analyzed for efficacy according to the treatment to which they were randomized.

6.3.3 Safety Population

The Safety Population is defined as all randomized subjects who have received at least one dose of study drug. All safety analyses will be performed on the Safety Population. In the

event of treatment allocation errors, subjects will be analyzed for safety according to the treatment group they received.

6.3.4 Per-Protocol Population

The Per-Protocol (PP) Population is defined as all randomized subjects who were compliant with study drug, completed at least 26 weeks of treatment or discontinued early due to hyperglycemia, and are a subset of the mITT Population. The PP Population will be used to assess robustness of the primary analysis results.

The following criteria may be evaluated for major deviations prior to unblinding the study database. A final listing of all subjects to be excluded from the PP Population will be completed prior to unblinding the study database.

- No eligibility criterion violations;
- Did not withdrawal prior to Week 26 if the reason is other than hyperglycemia;
- Subjects who did not miss more than 4 doses of study drug throughout the course of the study;
- Subjects who did not miss 2 consecutive doses of study drug during the dose escalation phase;
- Not taking any prohibited medications (treatment with medications that are excluded in the entry criteria is not permitted); and
- No other substantial protocol deviations.

6.4 Subject Disposition

Frequencies and percentages of all randomized, discontinued, and completed subjects in the study will be presented by treatment group and total. The reasons for discontinuations will be summarized by treatment group. Discontinuation rates will be compared between the treatment groups for each reason using a Fisher's exact test.

6.5 Demographic and Baseline Characteristics

Demographics and baseline characteristics will be summarized descriptively by treatment group and total for the ITT Population. If they differ from the ITT Population, summaries will also be provided for the mITT Population, PP Population, and Safety Population.

Demographic and baseline characteristics include, but are not limited to, age at informed consent, gender, race, ethnicity, body weight, BMI, BMI stratification group (<30 or ≥ 30 kg/m²), baseline HbA1c, HbA1c stratification group ($<8.5\%$ or $\geq 8.5\%$), and baseline FPG. The baseline is defined in Section 6.2, Baseline, Endpoint, and Other Statistical Considerations.

For categorical variables, comparisons between treatment groups will be assessed using a Pearson Chi-Square test. For continuous variables, comparisons between the treatment groups will be performed using a one-way Analysis of Variance (ANOVA) with treatment as the fixed effect.

6.6 Medical History

Medical/surgical history will be coded using the Medical Dictionary for Regulatory Activities (MedDRA) version 20.1. All medical history will be listed.

6.7 Prior and Concomitant Medications

Medication start and stop dates that are recorded on the Prior & Concomitant Medications case report form will be used to determine whether the medications are prior or concomitant to the study drug. Medications ongoing at the time of first dose of study drug (Visit 2 Week 0) as well as any new medication added during the course of the study will be considered concomitant medications. Prior medications are defined as those used prior to and stopped before the first dose of study drug. All prior and concomitant medication verbatim terms will be coded using the World Health Organization Drug Dictionary September 2017 Global B3 version. The numbers and percentages of subjects taking concomitant medications in each treatment group and in total will be summarized by anatomic therapeutic chemical term and preferred term for the Safety Population. All prior and concomitant medications will be listed.

6.8 Study Medication Exposure and Compliance

Subjects' exposure to study drug will be summarized with descriptive statistics for the Safety Population. Weeks of exposure is defined as:

$$(date\ of\ last\ dose\ of\ study\ drug - date\ of\ first\ dose + 1) \div 7$$

The total number of injections administered will be calculated for each subject. A contingency table will be provided to display the number and percentage of subjects in each treatment group with the following number of injections: 1-4, 5-8, 9-12, 13-16, 17-20, 21-24, 25-30.

Subjects that miss more than four doses of study drug over the course of study participation, or miss two consecutive doses of study drug during the dose escalation phase, are considered noncompliant. The frequency and percentage of subjects who are compliant and noncompliant will be summarized by treatment group.

6.9 Efficacy Analysis

6.9.1 Primary Efficacy Endpoint

The primary efficacy analysis is to evaluate the effect of dose escalation of OPK-88003 versus placebo injections on HbA1c absolute change from baseline to Week 30. If the Week 30 measurement is missing, the LOCF algorithm will be applied to impute the missing Week 30 value only for subjects that have early terminated due to hyperglycemia (Week 30/LOCF_H). Otherwise, no imputation will be made. The primary analysis will be based on the mITT Population. The same analysis will be repeated on the PP Population.

The change from baseline in HbA1c at each scheduled visit will be analyzed using a mixed-model repeated-measures (MMRM). The factors in the model will be BMI strata, treatment group, baseline HbA1c value, visit, and the treatment group by visit interactions. An unstructured covariance matrix will be used (TYPE=UN). No imputation will be performed except for subjects that early term due to hyperglycemia. The least-squares means for change from baseline at each visit will be estimated and compared between treatment groups, with Week 30 being primary, and no adjustments for multiplicity. The sample SAS code can be found below:

```
*****
Note:
  USUBJID = unique subject identifier
  TREATMENT = 0 (placebo), 1 (OPK-88003)
  BMI: <30 or >=30 kg/m2
  VISIT = visit
  BASE = baseline value
  CHG = change from baseline to the specified visit
*****;
proc mixed;
  class USUBJID BMI TREATMENT VISIT;
  model CHG = BMI TREATMENT BASE VISIT TREATMENT*VISIT;
  Repeated VISIT / TYPE=UN sub=USUBJID;
  lsmeans VISIT*TREATMENT / cl slice=VISIT;
run;
```

CCI

CCI [REDACTED]

Supportive Analysis

If the Week 30 HbA1c measurement is missing, the LOCF algorithm will be applied to impute the missing Week 30 value for all subjects (Week 30/LOCF_{All}). The change from baseline to Week 30/LOCF_{All} in HbA1c will be analyzed using linear contrasts from an analysis of covariance (ANCOVA) model with treatment group and BMI strata (<30, ≥30 kg/m²) as factors and the baseline HbA1c value as a covariate. The least-squares means, standard errors, and the 2-tailed 95% confidence intervals (CIs) for each treatment group and for comparison of OPK-88003 to placebo will be presented. The 2-sided p-values testing for significance within treatment group change from baseline and comparison between treatment groups will be presented.

The sample SAS code can be found below:

```
*****
Note:
  TREATMENT = 0 (placebo), 1 (OPK-88003)
  BASE: baseline HbA1c
  BMI: <30 or >=30 kg/m2
  CHG: change from baseline to Week 30/LOCF in HbA1c
*****;
proc glm;
  class TREATMENT BMI;
  model CHG = TREATMENT BASE BMI / ss1 ss3;
  means TREATMENT;
  lsmeans TREATMENT / cov stderr pdiff cl;
  estimate "OPK-88003 : Placebo" TREATMENT -1 1;
run;
```

Before this analysis is performed, the data will be inspected for normality and homogeneity of variance, and a non-parametric rank test will be applied if necessary.

The appropriateness of the statistical model will be evaluated by testing the treatment group by baseline HbA1c interaction at a significance level of 0.10. CCI [REDACTED]

